Guanfacine is the oldest alpha-2 adrenergic agonist in clinical use in this class.²⁴ Of the alpha-2 agonists, guanfacine has the lowest rate of sedation. 25 Guanfacine is currently approved in tablet form for the treatment of hypertension (1 to 2 mg) and Attention Deficit Hyperactivity Disorder (1 to 4 mg). Guanfacine is readily absorbed with around 80% oral bioavailability and has an elimination half-life of ~17 h with renal excretion accounting for ~50%. Guanfacine has been shown to have similar in vitro potency as clonidine to inhibit conduction in rat sciatic nerve fibers.²⁷ Intrathecal guanfacine has a similar antinociceptive effect as that of intrathecal clonidine in a goat model.²⁸ Guanfacine showed longer antinociceptive effect in comparison to clonidine (8 h vs. 5 h) due to slower elimination of guanfacine from spinal cord tissue. In a rat model, intrathecal guanfacine has shown antinociceptive effect for greater than 18 h (both 25 mcg and 50 mcg) in comparison to clonidine injection (50 mcg) which declined to baseline within 4 h.²⁹ This study also reported a lower rate of elimination of guanfacine from spinal cord tissue compared to clonidine. Highly concentrated guanfacine (75 mcg in 15 µl saline) solution administered through an intrathecal route has been shown to be nontoxic in the subarachnoid space, establishing the safe use of guanfacine for perineural blockade.³⁰ Guanfacine as studied in animals and used in humans has a safe risk profile, suggesting that repurposing it for other indications. Guanfacine has the potential to be developed as a safe, non-opioid, analgesic for acute and chronic debilitating pain. Guanfacine in combination with 1% lidocaine is expected to be safe and to provide an extended duration of pain relief in painful trigeminal neuropathy patients who are not able to obtain pain relief from standard neuropathic pain medication.

PheWAS data indicating the role of the alpha-2-adrenergic receptor in trigeminal nerve pain

BioVU is a large repository of de-identified DNA samples that Vanderbilt University Medical Center (VUMC) has cataloged for >10 years from what otherwise would have been excess, discarded patient blood samples collected during routine clinical testing. Biospecimens within BioVU are linked to corresponding longitudinal clinical and demographic data derived from the Synthetic Derivative, our de-identified database of EMRs. 31-33

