5.0 STUDY PROCEDURE

The study is a single center, randomized, double-blind, 2 x 2 crossover pilot study with two arms; study drug (guanfacine and lidocaine combination) and active control (lidocaine alone). Adult participants between 18 and 80 years of age who have been diagnosed with painful trigeminal neuropathy will be consented for the study. The study includes three visits; an initial visit for evaluation, consent, and baseline surveys followed by two procedural visits. After each procedural visit data will be collected for 14 days. Participants will be randomized in permuted pairs (to ensure balance after every second enrollment) to receive either study drug (guanfacine and lidocaine combination) or active control (lidocaine alone) for the first nerve block procedure. Following the first procedural visit and 14-day follow up period, the study team will assess inclusion and exclusion criteria and (if eligible) schedule the second procedural visit.

Assessment	Study Visit 1: Consent and screening (Day -15 to 0)	Study Visit 2: Procedure 1 (Day 1)	Follow-up period 1 (Day 2-14)	Study Visit 3: Procedure 2 (≥15 days after procedure 1)	Follow-up period 2 (14 days after procedure 2)
		Administrative P	rocedures		
Eligibility Review	X	X		X	
Informed Consent	X				
Demographics	X				
Pain History	X				
Baseline Pain	X	X	X	X	X
Medical History	X				
Concomitant Medications	X	X		X	
Surgical/ Past Treatments History	X				
Verbal Pregnancy Screen	X				
PROMIS Global 10- SF	X	X	X \$	X	X \$
Pain Interference	X	X		X	
Pain Intensity (VAS Score)	X	X #	X %	X #	X
Frequency of Attacks	X	X	X \$	X	X \$
Rescue Medications		X %	X %	X %	X
Randomization	X				
	Cl	inical Procedures/	Assessments		•
Physical Exam (general)	X	X		X	
Physical Exam (pain)	X				
Vitals (HR, RR, Temp, BP)	X	X		X	
Height/ Weight	X				
12-Lead ECG ^	X				
Continuous ECG monitoring		X		X	
Nerve Block Administration		X		X *	
Imaging MRI/ CT report +	X				
Adverse Events		X	X	X	X
		Laboratory Pro	cedures		
Urine Pregnancy Test		X		X	
Urine Drug Screen	X				

^{#:} Collected every 30 minutes for 8 hours by text message (REDCap) or patient diary

^{%:} Collected daily for up to 28 days by text message (REDCap) or patient diary

Collected weekly for up to 4 weeks by study nurse phone call

If pain score >5

^{+:} Review recent imagining, if not available then order as standard of care
^: Order 12-lead ECG as standard of care if one not available within 2 months of screening visit

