Participants will be asked to record their pain intensity, 24- hour VAS and current VAS, before the procedure to establish a baseline pain score. Other data will be collected for secondary measures: frequency of pain attacks, basal and breakthrough opioid and non-opioid analgesic frequency and dose. Overall quality of life (PROMIS Global-10 short form) will be assessed.³⁹ Women of childbearing potential will undergo a urine pregnancy test prior to receiving the nerve block.

First trigeminal nerve block procedure: Participant will receive either study drug (guanfacine and lidocaine combination) or active control (lidocaine alone) for the trigeminal nerve block based on randomization. Participants will be monitored for pain intensity at 30-minute time intervals for the first 8 hours after block in addition to safety monitoring procedures. Participant responses will be collected at 30 minute intervals for the first 8 hours while in the recovery (first 60 minutes) and after discharge home, with responses allowed all the way until the next time point and actual time of the response being used in analysis. Assessments will be recorded according to the patient's preference, either on paper or via text message) using the Twilio application linked to REDCap. Patients will also receive a sheet with contact information for the study nurse.

First follow-up period (Day 2 to Day 14)

Participants will be monitored once daily at approximately the same timepoint for 14 days using text message generated using the Twilio application or recorded on a paper diary. Participants will also be monitored for any use of rescue medication (analgesics) once daily. The study nurse will monitor participants once weekly for overall quality of life via phone call using the PROMIS global 10 SF. Participants will be instructed to contact the study nurse with any adverse events directly by phone.

At the end of the first follow-up period, participants will be contacted for crossover to the other arm to receive the second trigeminal nerve block using the alternative drug (study drug or active control), not received during the first nerve block. At the second study visit, participants will record 24-hour VAS and current VAS, and the PROMIS Global-10 Short Form to establish baseline measurement again. Women of childbearing potential will undergo a urine pregnancy test prior to receiving the nerve block.

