6.0 RISKS

During the consent process, study personnel will address potential discomfort and risks associated with the protocol. These will be included in the consent form.

Based on the known common side effects of the study drugs and the trigeminal block procedure, the following risk associated with participation in the study are perceived as low:

- Bradycardia
- Hypotension
- Dry Mouth
- Sedation
- Dizziness
- Headache
- Bruising, redness, itching, or swelling at the site of injection
- Intravascular injection resulting in seizure or stroke
- Bleeding
- Increased pain

In the event sedation or dizziness is observed after the procedure, standard of care practices for managing side effects will be performed, and the event will be documented and recorded according to the regulation.

It is understood that there may be as-yet unknown or unanticipated adverse effects of this study treatment. The study team will continually monitor for these effects and consider altering the protocol if needed to ensure patient safety. Changes in the procedures of the study, as well as any change(s) in the risks and/or benefits will be presented to and discussed with the subjects upon approval from the appropriate regulatory bodies for implementation of such revision(s).

Safety Monitoring:

Patients are examined on the day of the procedure to confirm the source of pain, vital signs are stable and in normal range, and female patients are confirmed not-pregnant through point of care pregnancy tests. During the procedure continuous pulse oximetry is used to monitor oxygenation, blood pressure is obtained every 2 minutes, and 3-lead electrocardiogram is monitored for heart rate and rhythm. Following the procedure, patients are taken to the recovery room adjacent to the procedure room to be monitored for 1 hour with continuous pulse oximetry, blood pressure (measured every 5 minutes), and continuous ECG to ensure stable vital signs. The patients are discharged home with a responsible adult after recovery. Before, during, and after the procedure patients are monitored by a registered nurse skilled in the evaluation of vital signs and familiar with the procedure. [name] is an Anesthesiologist and will be present for the duration of patient care.

Data Monitoring:

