The trigeminal block procedure is standard of care in the pain clinic. Expected effects of successful block include transient numbness, transient facial weakness including ipsilateral eyelid lag, and rare visual changes all of which resolve with the resolution of the effects of lidocaine over the typical course of 2 hours. Rare risks of the block procedure include infection, bleeding, nerve injury from the mechanical placement of the block needle. Rare risks of using lidocaine during the block procedure include intravascular or subdural injection resulting in transient unresponsiveness and/or seizure, mild sedation, bradycardia, and arrhythmias. These rare risks and side-effects must be differentiated from potential side-effects due to the addition of guanfacine. As all eligible patients are in

clinic for diagnostic nerve block as standard of care, they will receive clinical consent to treatment for the injection procedure itself and necessary x-ray radiation as part of routine care.

Common side-effects of daily oral use of guanfacine include dizziness, drowsiness, tiredness, low blood pressure, and slow heart rate. These side-effects are similar among other medications in the same class including clonidine, dexmedetomidine, tizanidine. Clonidine is also used as an intrathecal analgesic and as a perineural adjunctive injectate for regional blocks. We would expect that the side-effects of guanfacine as an adjunct to lidocaine block might additionally include increased dizziness, drowsiness, tiredness, low blood pressure, and slow heart rate. If the level of sedation experienced by at least 20% of patients in either group is greater than anticipated either by severity or duration, study enrollment will be stopped and the safety monitor engaged for an interim review of data comparing the study groups. If oversedation is occurring in only one group, an adjustment will be made to maintain monitoring for more than an hour (as is standard) until complete recovery.

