Potential adverse events (AE) including any occurrence of the above listed procedural or medicine-related side-effects and risks will be documented as AE's, described and categorized as mild-, moderate-, severe- AE and submitted for review by the safety monitor and IRB. The PI will also submit the likelihood of the AE being potentially related to the use of guanfacine. Severe AEs would include the occurrence of a seizure, severe sedation requiring ventilation support; bradycardia, unstable arrhythmias, or hypotension requiring resuscitation (medical or mechanical). The occurrence of a severe AE that is deemed study related would result in a stop of enrollment to report the data to the IRB, and FDA guidance would be obtained prior to study restart.

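### Fixed permuted pairs, printed in a single-center protocol, pass any correct identification of one participant's arm to the pair-mate; varying undisclosed blocks would reduce this at almost no cost

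*Combined protocol and SAP*

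**What the plan says.** Section 5.0 describes the design: "The study is a single center, randomized, double-blind, 2 x 2 crossover pilot study with two arms". The allocation rule follows: "Participants will be randomized in permuted pairs (to ensure balance after every second enrollment". That is a block of two, with one participant per sequence in each pair. At the end of the first follow-up the participant crosses over "to receive the second trigeminal nerve block using the alternative drug (study drug or active control), not received during the first nerve block".

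The schedule in Section 5.0 places randomization at Visit 1 (Day -15 to 0). Eligibility is reviewed at Visit 1 and again on both procedure days.

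The blinding safeguard described is in Section 3.0: the two syringes look the same. The documents describe no varying block size, no holder of the list, no concealment procedure and no check of the blind.

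On signs that staff could see, Section 7.0 (Safety Stopping Criteria) says side effects of the combination "might additionally include increased dizziness, drowsiness, tiredness, low blood pressure, and slow heart rate". Section 6.0 (Safety Monitoring) has these signs closely watched: during the procedure "blood pressure is obtained every 2 minutes", then every 5 minutes for an hour in recovery, with continuous ECG. Section 7.0 adds: "The PI will also submit the likelihood of the AE being potentially related to the use of guanfacine".

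**The concern.** With pairs, whatever is learned about the first member is learned about the second. One team at one site treats both and has the block size in its protocol. Identical syringes cannot hide a fall in blood pressure or a slow pulse, and asking the investigator to rate relatedness to guanfacine invites a guess at the arm.

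Staff who believe they know the pair-mate's sequence could be influenced at three points:

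- whether to enrol that person, if not yet randomized;
- the Day 1 eligibility review, which follows randomization and includes an investigator-opinion exclusion (Section 2.0);
- the relatedness rating of that person's adverse events.

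**Working it through.** The plan gives no predictability figure, so there is none to reproduce. Its power figure serves only to check what a different scheme would cost.

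**Planned power.** Inputs from Section 9.1: difference 28 minutes, within-subject SD 30 minutes, 30 participants. Section 9.0 gives the two-degree-of-freedom test at 5%. Noncentrality = 30 × 28² / (2 × 30²) = 13.07, and the noncentral chi-square gives 90.9%, in line with the stated figure of about 90%.

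**Cost of imbalance.** Variance ratio for 16:14 against 15:15 = (1/16 + 1/14) / (2/15) = 1.0045. Even dividing the noncentrality by this leaves 13.07 / 1.0045 = 13.01, so power is essentially unchanged.

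**Worst case: all earlier allocations known.** Count the positions at which only one arm remains in the block.

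- Pairs: 2 orderings × 2 positions = 4, of which 2 are determined: 50%. With the 40 participants that Section 2.0 expects to start, this is 20 of 40.
- Blocks of 4: 6 orderings × 4 positions = 24, of which 8 are determined: 33.3%.
- Blocks of 6: 20 orderings × 6 positions = 120, of which 30 are determined: 25%.
- Randomly varying 4 and 6, sizes withheld: about 5.5%, by simulation of lists of 40.

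**Imperfect guess.** Let q be the chance that staff read a treated participant's arm correctly, with readings independent and available before the next allocation. The documents give no rates for the signs, so q is an assumption. If a sign appears in a share p1 of guanfacine blocks and p0 of lidocaine blocks, q = 0.5 × p1 + 0.5 × (1 − p0). Assumed rates of 20%, 50% and 80% against 10% give q = 0.10 + 0.45 = 0.55, 0.25 + 0.45 = 0.70 and 0.40 + 0.45 = 0.85.

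Overall best-guess accuracy:

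- Pairs: the first member is a coin toss and the second is read with accuracy q, so (0.5 + q) / 2.
- Blocks of 4: by position 0.5, (1 + q)/3, (1 + q)/3 and q² + 2q(1 − q)², averaged. At q = 0.70: (0.5 + 0.567 + 0.567 + 0.616) / 4 = 56.2%.
- Blocks of 6: the same calculation over the 20 orderings.

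| q | Pairs | Blocks of 4 | Blocks of 6 | Gain over pairs (points) |
|---|---|---|---|---|
| 0.55 | 52.5% | 51.5% | 51.1% | about 1 |
| 0.70 | 60.0% | 56.2% | 54.9% | 4 to 5 |
| 0.85 | 67.5% | 62.4% | 59.8% | 5 to 8 |
| 1.00 | 75.0% | 70.8% | 68.3% | 4 to 7 |

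At q = 1, randomly varying 4 and 6 with sizes withheld gives about 69%. Varying sizes therefore remove most of the certainty, but less of the guessing advantage.

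**The case against.** The strongest reply is that the cues may be weak. Section 7.0 says only that side effects might include these signs, and it extrapolates from daily oral use. The trial gives one 250 mcg perineural dose, against the 1 to 4 mg of the approved tablets (Sections 3.0 and 1.0). Section 1.0 states: "Of the alpha-2 agonists, guanfacine has the lowest rate of sedation". Section 7.0 also lists, as rare risks of lidocaine itself, "intravascular or subdural injection resulting in transient unresponsiveness and/or seizure, mild sedation, bradycardia, and arrhythmias". This stands. It is why no single value of q can be defended and why the gain may be about 1 point.

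The timing also narrows the exposure. Because randomization is at Visit 1, the second of a pair may be randomized before the first is treated. That person's enrolment then cannot be steered, and only the Day 1 review and later ratings remain open. Day 1 eligibility rests largely on a self-reported pain score and a pregnancy test. For serious events, a Safety Monitor also assigns causality (Section 7.0), which is partial mitigation.

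A reader might infer three stronger things that the documents do not support:

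- **That pairs reveal both treatment periods.** A person's own second drug follows from the first in any 2 x 2 crossover. Likewise, by the second block staff have already seen that person's own first response, so the pair-mate adds little to decisions on progression.
- **That pairs create expectation effects in the self-reported primary outcome.** Nothing tells participants who their pair-mate is, and their own drowsiness would be equally revealing under any block size.
- **That half the allocations will be known.** That requires certain identification of every first member.

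None of this gives a reason to prefer pairs. Their one advantage, exact balance, is worth about 0.4% in variance, and dropout and replacement are likely to erode it.

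**Conclusion.** The point holds in a limited form. A disclosed block of two at one center is the most predictable blocked scheme available: a correct identification settles the pair-mate's sequence, and a guess carries over with its own accuracy. Moving to blocks of 4 or 6 lowers determined allocations in the worst case from 50% to 33% or 25%. It lowers best-guess accuracy by about 1 point with weak cues and by up to about 8 points over the range examined.

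This rests on an assumed q, on the first of a pair being treated before the second is handled, and on staff being able to tell who is paired. The last is uncertain: the data-monitoring text in Section 6.0 mentions randomization strata that are defined nowhere, and the sequence given to replacement participants is not stated.

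No bias in the 28-minute comparison has been shown. That comparison is mainly within-person, which limits selection bias, although participants with first-period data only are more exposed. The point is a low-cost improvement and does not affect the sample size.

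**What to change.** For all remaining allocations, replace permuted pairs with randomly varying block sizes, for example 4 and 6. Remove the block size from the protocol and record it only in a restricted document. State that the pharmacy or an independent statistician holds the list.

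The cost is a new randomization list and a short protocol edit. The sequences may finish slightly unbalanced, as in the 16:14 case above. The change does not remove a participant's ability to infer their own second treatment.

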2.0 STUDY DESIGN

Primary Hypothesis:

Due to its different but relevant mechanism of action, guanfacine will be an effective adjunct to lidocaine in trigeminal nerve block for the treatment of painful trigeminal neuropathy by enhancing and prolonging pain relief compared to lidocaine alone.

Endpoints

The following endpoints will be measured to evaluate the exploratory objectives of the study assessing guanfacine and lidocaine in combination compared to lidocaine alone, in pain management in the painful trigeminal neuropathy patient.

- Primary endpoint: time to return to baseline pain (VAS) measurement after treatment with guanfacine as adjuvant to 1% lidocaine compared to 1% lidocaine alone
- Safety endpoint: comparable side effect profile of combination product compared to lidocaine alone on relevant adverse event measures: sedation, local site reaction, confusion
- Secondary endpoint: pain intensity after treatment to be measured throughout the follow-up periods on a visual analog scale (VAS)
- Secondary endpoint: quality of life after treatment to be measured using PROMIS Global Health -10 SF during the follow-up periods
- Secondary endpoint: frequency of acute trigeminal nerve pain attacks during the follow-up periods
- Secondary endpoint: total amount of rescue medications (opioid and non-opioid analgesics) for pain management during the follow-up periods
- Secondary endpoint: time to first rescue medication during the follow-up periods

Experimental Design

The trial is designed as a single-center, randomized, double-blind, controlle, 2x2 crossover pilot study with two arms: study drug (guanfacine and lidocaine combination) and active control (lidocaine alone). The target sample size is 30 study drug vs. 30 active control.

Not all participants that are randomized and initiate the first arm of the trial will *necessarily* complete *both* arms of the crossover trial. Based on previous experience, initiating the first arm of the cross over trial in 40 participants should be sufficient reach the full sample size (30 study drug vs. 30 active control). The trial will be complete and enrollment will cease upon reaching the full proposed sample size (30 study drug vs. 30 active control).

Approximately 80 patients meeting preliminary enrollment criteria will be consented for screening with the goal of roughly half being eligible to randomize and begin participation in the trial.

Inclusion Criteria

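### Attack frequency, a secondary endpoint, is collected in follow-up only by a weekly nurse call; one item on the existing daily text would reduce recall error and keep the timing of any effect

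*Combined protocol and SAP*

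**What the plan says.** Section 2.0 lists, among five secondary endpoints, "frequency of acute trigeminal nerve pain attacks during the follow-up periods". In the schedule of assessments in Section 5.0, the attack row carries the same mark ($) as PROMIS in both follow-up columns. The footnotes for # and % keep their symbols, and the asterisk on the second block fits the footnote about a pain score above 5. That leaves $ for "Collected weekly for up to 4 weeks by study nurse phone call". The narrative agrees for PROMIS, which shares the mark: "The study nurse will monitor participants once weekly for overall quality of life via phone call using the PROMIS global 10 SF". It does not mention attacks in connection with that call.

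Pain intensity and rescue use have a daily channel. The schedule footnote reads "Collected daily for up to 28 days by text message (REDCap) or patient diary", and the narrative says "Participants will be monitored once daily at approximately the same timepoint for 14 days using text message generated using the Twilio application". Neither attaches an attack count to it. Attack frequency is otherwise marked only at screening and at the two procedure visits; for the first of these, the narrative groups it with the data taken before the block.

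On the length of follow-up, Section 5.0 says "After each procedural visit data will be collected for 14 days". The first follow-up period is headed Day 2 to Day 14.

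**The concern.** Without a log, an answer given by phone once a week is a recalled figure. If it covers the whole week, the participant must reconstruct up to seven days. If it covers less, the other days are not observed. The plan does not say which, does not define an attack, and does not say whether attacks on the block day after the injection count.

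A nerve block acts first on the hours after the injection. The background in Section 1.0 cites an elimination half-life of about 17 hours for guanfacine and animal antinociception of 8 hours and of more than 18 hours. If the adjuvant reduced attacks for hours or a day, a weekly total would average that reduction with days on which nothing differed, and could not show when it occurred. The channel that would avoid this is already running.

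**Working it through.** **1. The plan's own figure.** Section 9.1 gives about 90% power for the primary endpoint: 28-minute difference, SD 30 minutes between and within participants, 30 participants. The noncentrality is 28² / (2 × 30² / 30) = 784 / 60 = 13.07. The planned two-degree-of-freedom test then has 90.9% power (chi-square), and 90.2% in a simulation with estimated variance. The figure reproduces, and this point does not touch it. The plan gives no power for attack frequency.

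**2. Values per period.** 14 days / 7 = 2 calls per follow-up, so 4 over both periods. That matches the footnote's 4 weeks if it spans both periods, just as 2 × 14 = 28 matches the daily footnote's 28 days. The documents do not state this reading.

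**3. Dilution of a one-day effect.** Assume an even attack rate over days, and attacks halved on one day only:
- seen in that day's count: 50%
- seen in a weekly total: 0.5 / 7 = 7.1%
- seen in a 14-day average: 0.5 / 14 = 3.6%

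**4. Dilution of the planned effect.** Section 9.1 plans for 28 extra minutes and mentions 28 to 70. A day has 1,440 minutes, a week 10,080 and 14 days 20,160.
- 28 minutes: 1.9% of a day, 0.28% of a week, 0.14% of 14 days
- 70 minutes: 4.9%, 0.69% and 0.35%

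**5. What a daily count could gain.** A simulated paired comparison of attack counts used 30 participants, a two-sided 5% level and a t-test on square-root counts. None of the following assumptions is in the documents: 1, 5 or 20 attacks per day; between-participant coefficient of variation 0.6; period-to-period coefficient of variation 0 or 0.3; Poisson counts; no attacks at all during the extra relief; perfect recall; counting from the injection. Power over that range:

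| Extra relief | First-day count | First-week count | 14-day count |
|---|---|---|---|
| 28 min | 4–6% | about 5% | 5–6% |
| 70 min | 5–13% | 5–7% | 5–6% |
| 8 h | 23–100% | 6–53% | 5–30% |
| 24 h | about 100% | 20–100% | 10–99% |
| 48 h | about 100% | 66–100% | 28–100% |

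At 28 minutes no count does better than chance. The gain from day-level data appears at several hours to a day or two. Recall error is set to zero here, so the table shows dilution alone.

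**The case against.** The strongest reply is that the weekly call is not why the planned effect would be missed. At 28 to 70 minutes a daily count does hardly better, and short effects are measured elsewhere: VAS every 30 minutes for 8 hours, daily VAS, daily rescue use and time to first rescue. That stands, and it limits the point to a modest improvement. It does not remove the case for effects of hours to a day, which the background makes plausible although the sample size does not plan for them.

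Some stronger readings are tempting and should not be drawn:
- *That a weekly count cannot show a short-lived effect.* This is too strong. In the simulation a weekly count still has 20–100% power at 24 hours and 66–100% at 48 hours. What is lost in every case is the timing.
- *That a missed call costs half a period's data and a missed text only one fourteenth.* The comparison is not like for like. At equal miss rates per contact the expected fraction lost is the same, the documents give no miss rate for either channel, and a nurse can repeat a call.
- *That recall error costs a stated share of the sample size.* The documents give nothing from which to size it. Recall bias that is constant within a participant largely cancels in a blinded crossover; only random error remains.
- *That the narrative contradicts the schedule.* The statement "The study nurse will monitor participants once weekly for overall quality of life via phone call" does not rule out other questions. It is incomplete.

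A seven-day recall window and exactly two values per period are also inferences, the first because no window is stated, the second because attacks are marked at the second procedure visit as well.

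**Conclusion.** The point holds as a low-cost improvement to one secondary endpoint. On the natural reading of the footnotes, attack frequency in follow-up rests on about two recalled values per 14-day period, while a daily channel without an attack item is already in use. Recall error is avoidable but of unknown size. A one-day halving becomes about a 7% drop in a weekly total, assuming even attack rates, and its timing cannot be recovered. The power ranges depend on assumed attack rates and variability and indicate direction only. The planned 28 to 70 minute effect is out of reach for either method.

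**What to change.** - Add one item to the existing daily text or diary with a fixed window: *number of attacks in the past 24 hours*. A fixed window is better than counting since the last message, which brings back multi-day recall after a missed day.
- Start with the message that covers the hours after the injection on the block day, and say whether those hours belong to the endpoint. Define an attack.
- Analyse attacks per observed day over the same days in both periods. Report the first post-block day (or days 1 and 2) separately, because the 14-day average alone would dilute a one-day effect more than the weekly total does.
- Keep the weekly call for PROMIS.
- Reconcile the footnotes' 28 days and 4 weeks with the 14-day follow-up in the text.

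The cost is one REDCap/Twilio item, a footnote edit and a sentence in the analysis section, with no added staff, visits or participants. The downside is one more daily question, and some daily messages will be missed.
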